# **3 PARTICIPANT POPULATIONS**

#### **3.1 Population Definitions**

The following populations will be evaluated and used for presentation and analysis of the data:

- Enrolled Participants: Participants who signed an informed consent form and were assigned a Participant Identification number (PID)
- Randomized Participants: Enrolled participants who received a randomized treatment assignment. This group forms the ITT population
- Treated Participants: Enrolled and randomized participants who received at least 1 dose of blinded study therapy (BHV 4157 or placebo). This will be the primary analysis population used for safety summaries
- The modified Intent-to-Treat (mITT) population will include all randomized participants who took at least one dose of study medication, who have a baseline assessment of at least one of the co-primary endpoints, and who have at least one efficacy evaluation visit during the double-blind phase following baseline. This will be the primary analysis population used for the efficacy analyses.
- Treated Participants in Open Label Extension: Participants who received at least 1 dose of open label study therapy (BHV 4157) in the Extension Phase. This will be the primary analysis population used for safety summaries focusing on the Extension Phase
- The modified Intent-to-Treat (mITT) population for the Extension Phase will include all randomized participants who took at least one dose of open label study therapy (BHV4157) in the Extension Phase, who have a baseline assessment for the extension phase, and who have at least one efficacy evaluation during the extension phase. This will be the primary analysis population used for the efficacy summaries in the extension phase
- Treated Participants in All Troriluzole Exposure. Participants who received at least 1 dose of Troriluzole in either the Randomization Phase or the Extension Phase. This will be the primary analysis population used for safety summaries focusing on All Troriluzole exposure

The primary population for all efficacy analyses is the mITT population (subjects included in treatment group as randomized). The Treated Participants will be used for analyses of safety endpoints (subject included in treatment group as received).

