1.7.1 Adverse Event Profile

1.7.1.1 BHV-4157

Study BHV4157-201 was a double-blind, placebo-controlled study conducted with BHV-4157 to assess safety, tolerability and efficacy in participants with SCA, which is a progressive, genetic, degenerative neurological disease. Participants received BHV-4157 140 mg once daily or placebo for 8 weeks. A total of 141 participants were enrolled into the study. Overall, BHV-4157 140 mg once daily for 8 weeks was well tolerated in adult participants with SCA. The majority of adverse events were mild or moderate in severity. There were no deaths reported in this study. Treatmentemergent SAEs were reported for 5 (3.55%) participants, including 4 BHV-4157-treated participants (asthenia, atrial fibrillation, blood creatinine phosphokinase increased, dehydration, back pain and cerebral infarction), and 1 placebo-treated participant (chest discomfort). No SAE reported in the BHV-4157 group was judged by the investigator to be treatment related. The completion rate was 90.14% (64/71 participants) in the BHV-4157 group and 97.14% (68/70 participants) in the placebo group. The frequency of treatment-emergent AEs that led to withdrawal from study drug was 4.23% (3/71 participants) in the BHV-4157 group and no participant in the placebo group. The majority of treatment-emergent AEs during the Double-Blind Randomization phase (Safety Analysis Set) were mild or moderate in severity, not related to study therapy, and resolved spontaneously by the end of treatment. The most frequently (\geq 5%) reported treatment-emergent AEs were:

Treatment-emergent AE	Number of Participants (%)	Study Group
Dizziness	8 (11.27%)	BHV-4157
	1 (1.43%)	Placebo
Fatigue	6 (8.45%)	BHV-4157
	3 (4.29%)	Placebo
Fall	5 (7.04%)	BHV-4157
	1 (1.43%)	Placebo
Headache	4 (5.63%)	BHV-4157
	4 (5.71%)	Placebo
Nausea	4 (5.63%)	BHV-4157
	4 (5.71%)	Placebo
Muscle Spasms	4 (5.63%)	BHV-4157
_	2 (2.86%)	Placebo

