The Investigators at each site will make every reasonable effort to maximize participant retention, even if the study treatment is discontinued before week 48. However, if an investigator removes a participant from study, or if a participant declines all further study participation during the study, an Early Termination Visit will be completed as close as possible to the time of study discontinuation. The Early Termination Visit may contain the same assessments as week 48, to allow collection of the main outcome measures. For further detail please refer to the Procedures Manual.

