12.2 Analysis Populations

Analysis populations are defined as follows:

- Enrolled Participants: Participants who signed an informed consent form and were assigned a Participant Identification number (PID).
- Randomized Participants: Enrolled participants who received a treatment assignment. This
 group forms the ITT population.
- Treated Participants: Enrolled and randomized participants who received at least 1 dose of blinded study therapy (BHV-4157 or placebo). This will be the primary analysis population used for safety summaries.
- The modified Intent-to-Treat (mITT) population will include all randomized participants who took at least one dose of the study medication, who have a baseline assessment of

the co-primary efficacy endpoints, and who have at least one efficacy evaluation following baseline. This will be the primary analysis population used for the efficacy analyses.

- Open-Label Extension Treated Participants: Participants enrolled in the extension phase who received at least 1 dose of open-label extension phase study therapy (BHV-4157). This will be used for safety summaries of the extension phase
- The modified Intent-to-Treat (mITT) population for the Extension Phase will include all Open-Label Extension phase participants who took at least one dose of Extension phase study medication, who have at least one efficacy evaluation during the extension phase. This will be the analysis population used for the efficacy summaries for the extension phase
- All BHV-4157 Treated Participants: Participants enrolled who received at least 1 dose of BHV-4157 in either Randomization or Extension Phase of the study. This will be used for safety summaries of the extension phase

The primary population for all efficacy analyses in the double-blind treatment phase is the mITT population, without imputation for missing values. A sensitivity uses the mITT population with multiple imputation. The Treated Participants will be used for analyses of safety endpoints.

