#### Summary of primary estimand:

The effect relative to placebo of treatment as actually taken for 48 weeks during the doubleblind phase, in the protocol-defined mITT study population.

1. Objective

An estimate of efficacy which would potentially be supportive of registration; thus similar to an ITT, "as taken" estimand.

- 2. Estimand
  - A. The population is the mITT population as defined by the protocol's inclusion and exclusion criteria.
  - B. Efficacy is measured by the change from baseline to 48 weeks in the co-primary endpoints (ADAS-cog and CDR-SOB)
  - C. The treatment evaluated is the randomized treatment as it was assigned to study subjects. All types of intercurrent events are incorporated using a treatment policy strategy, which evaluates the randomized treatment as taken including missed or modified doses, drug discontinuation, and concurrent treatments. Study dropout including those potentially related to the COVID-19 pandemic (and corresponding discontinuation of assessments) will be handled by a hypothetical strategy to estimate what the outcome would have been at the designated time point if all subjects were continued to be assessed. Deaths are not expected during the 48 week double-blind phase follow-up in the enrolled subject population.

- D. The mean change from baseline between treatment and control arm on the 2 endpoints will be compared at 48 weeks between treatment and placebo arms. A significant difference in both endpoints at familywise error rate of 5% will be required for success.
- 3. Primary estimator and missing data.

The estimator is a MMRM using all available assessments. Under the assumption that data are MAR conditional on model covariates and observed assessments, this analysis estimates the treatment as taken in the mITT study population.

Note that MAR assumes that subjects will follow the same trajectory after dropping out of the study as while on the study, conditional on the model covariates. However, if subjects tend to preferentially drop out after discontinuation of study drug, their post-dropout trajectory (off treatment) may differ from their pre-dropout trajectory (on treatment). In this case the MAR assumption may not hold. A sensitivity analyses is proposed to assess this scenario.

4. Sensitivity analyses and missing data.

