MMRM, using multiple imputation from the control arm to complete assessments missing after discontinuation of study drug. This analysis assumes subjects who discontinue medication and are no longer assessed immediately become similar to subjects who never took any medication, and so provides a lower bound on efficacy, again under the MAR assumption that the time of stopping study medication depends only on past history and covariates

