#### 4.8 Efficacy Evaluation

Unless otherwise noted, all efficacy analyses will be conducted using all available in-clinic assessments from the mITT population during the double blind phase. Remote assessments during the double blind phase will be included in sensitivity analyses. All efficacy data will be included in listings by participant, treatment group, visit and phase (as applicable).

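### The placebo-based imputation labelled a lower bound on efficacy is run in mITT, so it omits randomised participants with no post-baseline efficacy evaluation

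*SAP*

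**What the plan says.** **Population.** Both documents define an ITT set of all randomised participants, but neither assigns an efficacy analysis to it. Efficacy is analysed in mITT. Under SAP 3.1 this needs a dose, a baseline on at least one co-primary endpoint, and participants "who have at least one efficacy evaluation visit during the double-blind phase following baseline". Protocol 12.2 has a similar condition: participants "who have at least one efficacy evaluation following" baseline.

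**Sensitivity analysis.** Protocol 12.2 is explicit: "A sensitivity uses the mITT population with multiple imputation". The SAP paragraph on imputation (4.8.3, sensitivity 1) names no population. It follows the methods of the primary analysis, and SAP 4.8 sets the default: "Unless otherwise noted, all efficacy analyses will be conducted using all available in-clinic assessments from the mITT population". The imputation is jump-to-reference, with parameters from the placebo arm. SAP 4.3.1.1 says it treats those who stop drug and are no longer assessed as if never medicated, "and so provides a lower bound on efficacy". SAP 4.8.3 repeats the label.

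**Timing.** ADAS-Cog 11 and CDR-SOB are first scheduled after baseline at Week 12 (Protocol 8.1.6; Appendix I, Table 1). The dose-escalation call is at Week 2 (8.1.3), and no efficacy scale is listed at Weeks 4 or 8.

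**Early termination.** Protocol Section 10 says "The Early Termination Visit may contain the same assessments as week 48". Protocol 8.1.9 and the schedule's combined Week 48/Early Termination column list ADAS-Cog 11 and CDR-SOB without that reservation.

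**The concern.** The imputation exists to show how far the efficacy estimate could fall if dropouts lose all benefit. A participant who leaves with no post-baseline evaluation is the most complete case of dropout, and the mITT filter removes that person before anything is imputed. The filter acts after randomisation, and tolerability can influence it.

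What is at stake is the meaning of the bound. SAP 4.3.1.1 states an objective of supporting registration, "thus similar to an ITT". A reader could take the lower bound as holding for everyone randomised, when it holds only for those with at least one evaluation. Among all randomised participants the same method would give a smaller effect.

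**Working it through.** **Inputs.** From Protocol 12.1.1 and SAP 4.2: 168 randomised per arm, 26% dropout, 124 per arm at the final analysis, differences of 2.64 (SD 6) on ADAS-Cog 11 and 0.95 (SD 2.3) on CDR-SOB, correlation 0.45, probability 0.937 of passing the interim. From Protocol 1.7.1.1, on Study 201: "The completion rate was 90.14% (64/71 participants) in the BHV-4157 group and 97.14% (68/70 participants) in the placebo group". Not given: e, the share of the active arm outside mITT. It is varied below.

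**Step 1. The plan's own figures.** With 124 per arm and a two-sided 5% test, power is 93.4% by the normal approximation (93.2% by the exact t) for ADAS-Cog 11, against 92% stated. For CDR-SOB it is 90.2% (90.0%), against 90%. Joint power with correlation 0.45 is 85.7%, and 0.857 × 0.937 = 80.3%, against 80%. The figures reproduce, and this point does not touch them.

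**Step 2. The ratio.** Let m be the expected placebo-based effect in mITT. Excluded active participants, imputed wholly from placebo, contribute about zero. Then

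all-randomised effect = (1 − e) × m + e × 0 = (1 − e) × m,

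so the mITT estimate is larger by a factor of 1/(1 − e). This ratio depends on neither the assumed effects nor the 26%. The placebo share excluded does not enter either, because imputing placebo participants from their own arm leaves the expected placebo mean about unchanged.

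**Step 3. In points.** Assume the design effects hold in completers and are zero in all active dropouts. With everyone kept, the effect is 0.74 × 2.64 = 1.95 and 0.74 × 0.95 = 0.70. In mITT it is 0.74/(1 − e) times the design effect.

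| Assumed e | Active participants excluded (of 168) | ADAS-Cog 11 | CDR-SOB | Excess over all randomised |
|---|---|---|---|---|
| 0 | 0 | 1.95 | 0.70 | none |
| 2% | 3.4 | 1.99 | 0.72 | +2.0% |
| 4.2% (3/71) | 7.1 | 2.04 | 0.73 | +4.4% |
| 5% | 8.4 | 2.06 | 0.74 | +5.3% |
| 9.9% (7/71) | 16.6 | 2.17 | 0.78 | +10.9% |

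The 4.2% row uses the active-arm rate of withdrawal from drug for adverse events in Study 201. The 9.9% row treats every active non-completer there as having no evaluation here.

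**Step 4. Scale.** The standard error implied by SD 6 and 124 per arm is 6 × √(2/124) = 0.76 points. The largest shift in the table is about 0.21 points on ADAS-Cog 11, or 0.28 of a standard error. At e = 5% it is about 0.10 points, or 0.13.

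**The case against.** The strongest reply is that few participants will be lost. Protocol 8.1.9 and the schedule place both co-primary scales at early termination. The Week 12 analysis window opens on Day 2, or Day 3 for CDR (SAP 4.3.8, Table 1), so an assessment at an early exit counts. Participants who stop drug are encouraged to stay for visits (Protocol Section 10). This stands. It means that two stronger readings fail.

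- A reader might infer that everyone who stops before Week 12 is excluded, leaving a set that tolerated the drug. Only those with no evaluation at all are lost.
- A reader might infer that the bound is 11% too favourable. That figure equates non-completion in Study 201 with having no efficacy data here. Study 201 was an 8-week trial in spinocerebellar ataxia at 140 mg. The dose and the time to first evaluation differ here, so its rate does not transfer directly. It shows only that early loss can be appreciable and unequal between arms.

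A second reply is that the estimand's population is mITT and study dropout has a hypothetical strategy, so a bound within mITT answers the stated question, and an all-randomised run changes the population as well as the imputation. That is fair as far as it goes. It supports qualifying the label if the population stays, but does not support an unqualified bound beside an ITT-like objective.

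Third, SAP 4.6 tabulates randomised, treated and mITT counts by arm. Unequal exclusion would be visible, but its effect on the estimate would not be shown.

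**Conclusion.** The point holds as a limited one. The placebo-based imputation bounds efficacy within mITT, not among all randomised participants, and its estimate is larger than the all-randomised one by about 1/(1 − e). The excess is 2% to 5% for e between 2% and 5%; about 11% is an upper-range illustration. The size rests on two assumptions: that excluded active participants would be imputed at about placebo level, which is what the method does, and a value of e that the documents do not supply.

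A reader might also infer that the primary result is biased by the same route. The documents do not support that. A participant with no post-baseline value contributes nothing to the MMRM of change scores, and success depends on that model and the gatekeeping order, not on this sensitivity analysis.

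**What to change.** 1. In SAP 4.8.3 (sensitivity 1) and Protocol 12.2, run the placebo-based imputation in all randomised participants with a baseline score on the endpoint, imputing every post-baseline visit where none was observed. The imputation model already carries baseline covariates. Keep mITT for the primary MMRM.
2. If the imputation stays in mITT only, state in SAP 4.3.1.1 and 4.8.3 that the lower bound applies within mITT.
3. Reconcile the permissive early-termination sentence in Protocol Section 10 with Protocol 8.1.9 and the schedule, which list ADAS-Cog 11 and CDR-SOB at that visit.

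The cost is one population flag in one program and minor wording in the SAP and protocol. The protocol wording goes through the amendment approvals in Protocol 5.2. The sensitivity estimate will be slightly less favourable.

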#### **3.2 Protocol Deviations**

Any significant event that does not comply with the inclusion/exclusion criteria, study conduct (e.g., inadequate informed consent, unreported SAEs), or study procedures (e.g., use of

prohibited medications as defined by the protocol; improper breaking of the blind) will be documented as a protocol deviation.

The sponsor, or designee, will be responsible for producing the final protocol deviation file (formatted as a Microsoft Excel file), which will be finalized prior to database lock. Classification of deviations from the protocol as minor or major will be decided on a case-by-case basis by the medical monitor without knowledge of the treatment assigned and before the database lock (Data Blind Review). This file will include site, participant ID, deviation date, deviation type, status (major vs. minor), and a description of the protocol deviation.

All protocol deviations will be presented in a tabulation and data listing. Both the summary tabulation and the listing will include information regarding whether the deviation was potentially related to the COVID-19 global pandemic.

## **4 STATISTICAL METHODS**

#### 4.1 Sample Size Justification and Power

#### 4.2 Overall Study Power

Using approximately 336 randomized participants (with a 1:1 assignment approximately 168 per arm), this study has at least 80% power to reject the null hypothesis of no efficacy in favor of the alternative that BHV4157 is efficacious, given the assumption of a difference in the mean change from baseline to 12 months between the BHV-4157 arm and placebo arm of 2.64 points on the ADAS-Cog 11 and 0.95 points in CDR-SOB, and under a range of interim effect sizes which give 93.7% probability of proceeding at the interim analysis.

This calculation assumes no more than a 26% dropout rate, which would leave  $336 \times 0.74 = 248$  subjects available at the final analysis, or 124 per arm. The calculation also assumes a standard deviation of 6 points on the change in ADAS-Cog 11 in each arm at both 6 months and 12 months, and a standard deviation of 2.3 points on the change in in CDR-SOB at 12 months; in addition a correlation of 45% between 12-month-change on the co-primary ADAS-Cog11 and CDR-SOB endpoints is assumed. These assumptions are supported by published retrospective data from historical ADCS studies. The computations use a 2-sided 2-sample t-test at 5% alpha to approximate power.

Briefly, the statistical reasoning is as follows:

- 1. P(pass overall) = P(pass final | pass interim) P(pass interim) ≥ P(pass final) P(pass interim)
- 2. P(pass final) = P(pass final ADAS) P(pass final CDR | pass final ADAS)
- 3. Numerical integration shows that P(pass final CDR | pass ADAS) is about 3% greater than P(pass final CDR), given the assumed 45% correlation between these endpoints.

Hence, if P(pass interim) = 0.937, P(pass final ADAS) = 0.92, and P(pass final CDR) = 0.90, then P(pass overall)  $\ge 0.92 \text{ x} (1.03 \text{ x} 0.90) \text{ x} 0.937 = 0.80.$ 

With 124 subjects per arm, the unconditional power for the ADAS-COG endpoint is 92%, if the mean difference in change is 2.64 points with standard deviation of 6 points within each arm. At this sample size, the unconditional power for the CDR-SOB endpoint is 90%, if the mean difference is 0.95 points with standard deviation of 2.3 points within each arm. Hence, if the interim analysis has power 0.937 or greater to pass, the overall power is 80% or more following the statistical reasoning given above.

For perspective, we note that the assumed difference of 2.64 points on ADAS-Cog is 68% of the decline observed in the placebo arm of 3.9 points in studies of mild to moderate  $AD^{14}$ . The assumed difference of 0.95 points on CDR-SOB is 59% of the decline observed in the placebo arm of 1.6 points.

#### 4.3 General Statistical Methods and Data Handling

#### 4.3.1 General Methods

#### Overview

The primary study hypothesis is that treatment with BHV-4157 will result in a reduction in total within-participant change from baseline on the ADAS-Cog 11 score and also on the CDR Sum of Boxes, relative to the placebo group at week 48 in the mITT population. The co-primary endpoints at the final analysis will be tested using a hierarchical gatekeeper strategy: if ADAS-Cog 11 is significant at the 5% level, then CDR-SOB will also be tested at 5% significance level. If ADAS-cog is not significant at the 5% level, then CDR-SOB will not be included in the primary analysis, and will be presented for descriptive purposes only. The primary objective of the trial is met only when both co-primary endpoints are significant. If both co-primary endpoints are significant, the remainder of the secondary endpoints will be tested at overall 5% significant, the secondary endpoints will be presented for descriptive purposes only. This will preserve alpha at 5% overall for all endpoints tested. Both the interim and final analysis will use a mixed effects repeated measures model. The secondary endpoints will compare mean changes from baseline to week 48 using a similar analysis strategy.

#### 4.3.1.1 Estimands, Intercurrent Events, and Missing Data

This discussion follows the framework as in Ratitch et al..

#### Summary of primary estimand:

The effect relative to placebo of treatment as actually taken for 48 weeks during the doubleblind phase, in the protocol-defined mITT study population.

1. Objective

An estimate of efficacy which would potentially be supportive of registration; thus similar to an ITT, "as taken" estimand.

- 2. Estimand
  - A. The population is the mITT population as defined by the protocol's inclusion and exclusion criteria.
  - B. Efficacy is measured by the change from baseline to 48 weeks in the co-primary endpoints (ADAS-cog and CDR-SOB)
  - C. The treatment evaluated is the randomized treatment as it was assigned to study subjects. All types of intercurrent events are incorporated using a treatment policy strategy, which evaluates the randomized treatment as taken including missed or modified doses, drug discontinuation, and concurrent treatments. Study dropout including those potentially related to the COVID-19 pandemic (and corresponding discontinuation of assessments) will be handled by a hypothetical strategy to estimate what the outcome would have been at the designated time point if all subjects were continued to be assessed. Deaths are not expected during the 48 week double-blind phase follow-up in the enrolled subject population.

- D. The mean change from baseline between treatment and control arm on the 2 endpoints will be compared at 48 weeks between treatment and placebo arms. A significant difference in both endpoints at familywise error rate of 5% will be required for success.
- 3. Primary estimator and missing data.

The estimator is a MMRM using all available assessments. Under the assumption that data are MAR conditional on model covariates and observed assessments, this analysis estimates the treatment as taken in the mITT study population.

Note that MAR assumes that subjects will follow the same trajectory after dropping out of the study as while on the study, conditional on the model covariates. However, if subjects tend to preferentially drop out after discontinuation of study drug, their post-dropout trajectory (off treatment) may differ from their pre-dropout trajectory (on treatment). In this case the MAR assumption may not hold. A sensitivity analyses is proposed to assess this scenario.

4. Sensitivity analyses and missing data.

MMRM, using multiple imputation from the control arm to complete assessments missing after discontinuation of study drug. This analysis assumes subjects who discontinue medication and are no longer assessed immediately become similar to subjects who never took any medication, and so provides a lower bound on efficacy, again under the MAR assumption that the time of stopping study medication depends only on past history and covariates

